8. INTERVENTION DISCONTINUATION

This study will be stopped prior to its completion if: (1) the intervention is associated with adverse effects that call into question the safety of the intervention; (2) any new information becomes available during the trial that necessitates stopping the trial; or (3) other situations occur that might warrant stopping the trial.

9. STATISTICAL CONSIDERATIONS AND DATA ANALYSES

We will conduct both intent-to-treat (ITT) and per protocol analyses. ITT includes all participants that were randomized, regardless of compliance, withdrawal, and other events after randomization. A strength of ITT is that it is based on original randomization. However, effect estimation using ITT may be conservative and misleading with increasing attrition. Per protocol analysis considers only participants who fully complied and completed the study. Per protocol is less conservative and may reflect true treatment differences for those with full compliance. Including both approaches will provide a more complete understanding of treatment effects.

Analyses will be performed using SAS. Descriptive statistics for all measurements will be reported. Frequency distributions will be created to screen for any coding or entry errors. Frequency distributions summarize categorical data, and measures of central tendency and dispersion will summarize continuous data. All data will be examined for bivariate relationships with the outcomes and with each other. All analyses will control for demographics (age, gender, race/ethnicity, education level, partner status) and baseline nicotine dependence (cigarettes per day and time to first cigarette). The overall study level of significance will be α =.05.

Aim I. Test the efficacy of a mindfulness-based text messaging program for smoking cessation ("iQuit Mindfully"), both as a standalone intervention and in combination with virtual counseling.

The relationship between treatment condition and each dichotomous study outcome (smoking cessation, lapse recovery) will be assessed with a generalized linear mixed model (GzLMM) with a Binomial distribution and logit link function. This is an appropriate statistical model with repeated measures data collected over time. ⁴⁴ A 2-level multilevel GzLMM will be specified, with time nested within subject. This approach will properly account for the multilevel data structure. Fixed effects considered in each model will include demographics, baseline nicotine dependence, treatment condition and time as main effects, and a treatment condition by time interaction. Testing of covariance structure will be conducted, and information criteria will be used to assess model fit and selection. Linear contrasts will be built into the analysis to estimate specific comparative effects of all treatment conditions. To test treatment effects on primary smoking cessation outcomes, repeated measures outcomes will be biochemically-confirmed 7-day point prevalence abstinence at weeks 8, 12, and 24. To test treatment effects on lapse recovery, this analysis will also be conducted among participants classified as smoking at the last treatment session. ¹² In addition, gender and race/ethnicity will be assessed as potential moderators of treatment effects.

The moderating effect of poverty status will be examined with the addition of a poverty status by treatment condition interaction into the models described in 1a). This will be tested using both dichotomous (i.e., below vs. at or above federal poverty threshold) and continuous poverty status variables (i.e., depth of poverty as indicated by income-to-poverty ratio and income deficit/surplus) according to U.S. Census guidelines.^{45,46}

Aim II. Investigate the mechanisms through which mindfulness training impacts smoking cessation.

Hypotheses regarding mechanisms will be tested with both traditional questionnaire data (collected from baseline through 24 weeks after the start of treatment) and electronic diary data (collected for 6 continuous weeks during treatment), separately. Mediation testing will be conducted regardless of statistical significance of intervention effects because of statistical, conceptual, and practical reasons for testing mediation in such cases.⁴⁷ Volatility will be calculated using the mean square successive

difference (MSSD; 48 average of the squared difference between successive observations at times i + 1 and i) to capture both within-person variability and temporal instability. Mediation will be examined with multilevel mediation analyses for binary outcomes in the developed GzLMM. Bootstrapping with 5000 replications will be used to estimate standard errors and p-values for indirect effects. In addition to mediators of associations between treatment and abstinence outcomes, we will test more fine-grained day-to-day associations using electronic daily diaries.

We will test moderated mediation using a model proposed by Preacher, Rucker, and Hayes⁴⁹ that fits the hypothesized model (Figure 3), as the independent variable (mindfulness training) also functions as a moderator. Kline⁵⁰ termed this "second-stage moderation," as the second path of the indirect effect of the predictor on the dependent variable depends on the moderator. Conditional mediation and moderation effects will be tested using bootstrapping methods.⁴⁹ GzLMM provides an ideal method for assessing the proximal relation between negative affect/craving at a given assessment and smoking at the next assessment (using both questionnaire and daily diary data). For example, using daily diary assessments, we will examine whether the association between negative affect on a given day and next-day smoking is weaker among MBAT vs. UC participants.

Missing Data. Although there is no complete, comprehensive method for handling missing data for generalized linear mixed models, there are several different approaches that we can draw upon to address this issue.⁴⁴ We will use multiple imputation of missing data whereby missing observations for individuals are estimated based on baseline responses and other study covariates, and perform additional sensitivity analyses regarding various missing data assumptions for smoking outcomes.⁵¹

Power and Sample Size Determination. Sample size was estimated based on the number of participants needed to detect meaningful treatment effects of the iQuit Mindfully and MBAT interventions. We obtained effect sizes (converted to Cohen's *d* for comparability across measures) from relevant meta-analyses and used the Optimal Design program to estimate sample size for GzLMM models. Samoking abstinence in MBIs vs. UC was quantified as *d*=0.35 in a meta-analysis, and a Cochrane review of primarily text messaging-based interventions for smoking cessation concluded an effect size of *d*=0.33. Assuming 80% power, level of significance of .05, two-tailed statistical tests, error variance of 1.0, coefficient variance of 2.0, and oversampling to account for 20% attrition, this results in 145 participants in each treatment group. An unequal allocation ratio was used to allocate fewer participants to usual care (*n*=50), 55,56 for an overall sample size of 485 participants (145 per treatment group and 50 in usual care). We expect this sample size to adequately allow for mediational testing (Aim 2) at the 80% power level. Fritz and MacKinnon for offer a guide regarding sample size required to detect mediated effects and report that 79.9% of studies in their literature review applied mediational testing with less than 400 subjects, suggesting our study plan with 485 subjects will be ample for achieving all study aims.

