1. STUDY OBJECTIVES

Study aims are to test the efficacy of a mindfulness-based text messaging program for smoking cessation ("iQuit Mindfully"), both as a standalone intervention and in combination with in-person counseling, and examine underlying mechanisms of mindfulness treatment. Approximately 485 participants (maximum 500) will be randomized to one of four groups:

- Usual Care (self-help materials + nicotine patch treatment)
- MBAT (8 weekly virtual MBAT sessions + self-help materials + nicotine patch treatment)
- iQuit Mindfully (iQuit Mindfully text messages + self-help materials + nicotine patch treatment)
- MBAT + iQuit Mindfully (8 weekly virtual MBAT sessions + iQuit Mindfully text messages + self-help materials + nicotine patch treatment)

All study participants will receive self-help smoking cessation materials, including the "Clearing the Air" booklet developed by the National Cancer Institute (NCI) and a referral to the Tobacco Cessation Quitline ([name]). All study participants will also receive nicotine patches. Assessments will occur at baseline and weeks 1, 3, 5, 8, 12, and 24. Primary outcomes are smoking abstinence at 8 weeks after the start of treatment (7-day abstinence, biochemically verified by expired carbon monoxide <6 ppm), 12 weeks after the start of treatment (3 month follow-up; 7-day abstinence, biochemically verified by expired carbon monoxide <6 ppm), and 24 weeks after the start of treatment (6-month follow-up; 7-day abstinence, biochemically verified by saliva cotinine < 20 ng/ml). Secondary outcomes include frequency of home mindfulness practice and self-reported levels of mindfulness, emotions, craving, withdrawal, dependence, self-efficacy, and social support. Aims and hypotheses are outlined below:

Aim I. Test the efficacy of a mindfulness-based text messaging program for smoking cessation ("iQuit Mindfully"), both as a standalone intervention and in combination with in-person counseling.

We hypothesize that:

- 1a) MBAT + iQuit Mindfully will result in higher rates of smoking cessation and lapse recovery than MBAT, which will produce higher cessation and lapse recovery than UC. iQuit Mindfully as a standalone intervention will also produce higher cessation and lapse recovery than UC.
- 1b) As an exploratory aim, we will examine whether poverty status moderates treatment efficacy (i.e., poverty status will predict worse cessation outcomes in MBAT but not MBAT + iQuit Mindfully).

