For our previous smoking cessation study at GSU, the inclusion criteria were slightly more rigid. For example, interested individuals were excluded if they also used tobacco products other than cigarettes. Given that use of other tobacco products (e.g., cigars, little cigars, cigarillos) is common among low-income adult smokers, we believe it is important to include these people and help them quit smoking cigarettes as well as other tobacco products. Accordingly, we will contact individuals who expressed interest in our previous smoking cessation study and did not qualify at that time but might meet the current eligibility criteria. We will describe the current study and if they are interested, they will complete the same screening procedures as other potential participants.

Randomization. Randomization will take place at the end of the baseline session, after baseline assessments have been administered. Stratified permutated block randomization will be implemented. Block randomization can achieve balance in the number of assignments to each treatment group. This form of randomization can be conducted within each stratum (i.e., stratified permutated block design) in efforts to achieve both covariate balance and treatment balance. To Given the dangers of overstratification (e.g., with too many strata, there may be insufficient numbers of participants within each block), researchers have recommended using one or two stratification variables that are expected to be most strongly associated with the outcome. To Stratification will be conducted with respect to race/ethnicity and poverty status, both of which are predictors of smoking cessation success.

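### The primary model adjusts for race/ethnicity but not for poverty status, the other factor that randomisation is stratified on

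*Combined protocol and SAP*

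**What the plan says.** Section 4 (Randomization) uses stratified permuted blocks. It warns against too many strata and gives its rule for choosing factors: "researchers have recommended using one or two stratification variables that are expected to be most strongly associated with the outcome". It then applies the rule: "Stratification will be conducted with respect to race/ethnicity and poverty status, both of which are predictors of smoking cessation success". It does not state the cut that defines poverty status for this purpose.

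Section 9 sets one covariate list for everything: "All analyses will control for demographics (age, gender, race/ethnicity, education level, partner status) and baseline nicotine dependence". Under Aim I it describes the primary model in the same terms: "Fixed effects considered in each model will include demographics, baseline nicotine dependence, treatment condition and time as main effects", together with a treatment-by-time interaction.

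Poverty status appears in Section 9 only for hypothesis 1b: "The moderating effect of poverty status will be examined with the addition of a poverty status by treatment condition interaction into the models" used for 1a. Section 1 sets the rank of that analysis: "As an exploratory aim, we will examine whether poverty status moderates treatment efficacy". Nothing in the document says that the primary model adjusts for the stratification factors, or why one of them is left out.

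**The concern.** The plan picks poverty status as a stratifier because it expects it to predict the outcome, then omits it from the model for that outcome. Stratifying makes the arms more alike on poverty than chance would. If the model does not contain poverty, its standard error does not reflect that extra balance, so the test rejects too rarely under the null and has less power than the design could give.

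There is a second consequence for 1b. The interaction is described as an addition to the 1a models, and those have no poverty main effect. Taken literally, the interaction coefficients would carry poverty's ordinary association with quitting as well as any difference between arms.

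**Working it through.** **1. The texts side by side**

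| Factor | Stratifies randomisation (Section 4) | Covariate list (Section 9) | Aim I fixed effects (Section 9) |
|---|---|---|---|
| Race/ethnicity | yes | yes | yes, as a demographic |
| Poverty status | yes | no | no; only in 1b |

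Education level is on the list, but it is only a partial stand-in for poverty.

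**2. Inputs for the size of the loss**

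The plan gives no figure on this point to reproduce. From the sample-size paragraph I take the arm sizes (3 × 145 + 50 = 485, as stated) and the effect sizes d = 0.33 and 0.35. On the odds-ratio scale, exp(d × π/√3) gives 1.82 and 1.89. The documents state neither an abstinence rate in the control arm nor the strength of the poverty association, so both are assumptions, shown over a range. The absolute power levels below follow from those assumptions and from using one time point; only the differences matter here.

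**3. Poverty acts equally in both arms**

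Assumed: 145 vs 145, 15% control abstinence, treatment odds ratio 1.9, half the sample in poverty and balanced between arms, ordinary logistic regression, two-sided 5% test.

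| Poverty divides odds of quitting by | Power, poverty omitted | Power, poverty included | Difference (points) |
|---|---|---|---|
| 2 | 55.7% | 56.7% | 1.0 |
| 3 | 54.0% | 56.1% | 2.1 |
| 5 | 49.8% | 53.5% | 3.7 |

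With no treatment effect, 6,000 trials of this set-up rejected in 4.7% vs 4.9%, 4.4% vs 4.8% and 3.8% vs 4.8% (omitted vs included). Omission makes the test conservative, not liberal.

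**4. Other assumptions, including the usual-care contrast**

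Assumed: permuted blocks within race/ethnicity by poverty strata, race/ethnicity in the model, 20% control abstinence, treatment odds ratio 1.85, 4,000 trials per row.

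| Poverty odds divisor | 145 vs 145: omitted / included | 145 vs 50: omitted / included |
|---|---|---|
| 1.5 | 61.3% / 61.7% | 32.3% / 33.0% |
| 2 | 61.5% / 62.6% | 31.1% / 32.4% |
| 4 | 56.0% / 59.4% | 28.4% / 32.3% |
| 8 | 50.4% / 58.0% | 25.2% / 32.7% |

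The pattern is the same: about 1 point at weak associations, 3 to 4 points at a divisor of 4, and more only at an extreme association.

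**5. Poverty acts only in the arm without text messages**

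This is what the pilot in Section 2 reports. With the inputs of step 3 and 20,000 trials, power was 55.7% vs 56.2%, 54.0% vs 54.7% and 50.9% vs 51.9% at divisors 2, 3 and 5. The gain is at most 1 point.

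**6. The literal form of 1b**

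With four arms, an interaction without a poverty main effect has four coefficients, one poverty effect per arm. The 4-degree-of-freedom test then asks whether poverty matters in any arm. With the main effect present, the test has 3 degrees of freedom and asks whether poverty's effect differs between arms. I took 145/145/145/50 participants, 20% usual-care abstinence, a treatment odds ratio of 1.85, half in poverty, and no moderation at all. The literal test rejected in 36%, 79% and over 99% of trials at poverty divisors 1.5, 2 and 3. The test with the main effect rejected in 5 to 6%.

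**The case against.** The strongest case against is that very little is lost.

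- Analysis is by intention to treat on the randomised arms, and race/ethnicity is already adjusted for. A reader might infer that the primary comparison departs from the randomisation, or that its error rate is inflated. The documents support neither: participants are compared by assigned arm, and the error is on the conservative side. This part stands in full.
- A reader might also infer that the treatment odds ratio will be pulled toward 1. That happens in a single-time logistic fit, but the plan is a two-level mixed model over weeks 8, 12 and 24. If its second level is a subject random intercept, that term takes up most of the omitted variation. A simulation of that case (145 vs 145, three occasions, assumed intercept SD 2.5, true log odds ratio 1.79, 250 trials) gave mean log odds ratios without vs with poverty of 1.79 vs 1.80 when poverty divides the odds by 9, and 1.83 vs 1.85 when it divides them by 25. I therefore make no claim of shrinkage. A loss of precision remained: median z was 3.96 vs 4.22 and 3.66 vs 4.08.
- The pilot found poverty unrelated to quitting among those who received the messages. This limits the gain for MBAT against MBAT + iQuit Mindfully (step 5). It does not settle the usual-care contrasts, and Section 4 calls poverty a predictor without that restriction.
- Most analysts would add the main effect when fitting 1b. That is likely, and the text does not forbid it, so step 6 does not show that 1b will be mis-tested. It shows what the wording permits.

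**Conclusion.** The inconsistency is real and sits in current text: one of two stratification factors, called prognostic by the plan itself, is missing from the primary model. The primary test remains valid. The cost is a slightly conservative test and about 1 to 4 points of power at poverty odds divisors of 2 to 5, less if the effect is confined to the arm without messages. These figures rest on assumed abstinence rates, an assumed half of the sample in poverty, a single time point and no attrition. Education level, already in the model, would take up part of the loss. The wording of 1b needs the same correction. This is a minor point, worth making because the repair is almost free.

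**What to change.** In Section 9, add poverty status, coded as it was for stratification, to the covariates for all analyses, and name it as a main effect in the Aim I mixed model. The primary and 1b models then share the same main effects. Where 1b uses a continuous poverty measure, state that its main effect enters with the interaction. In Section 4, state the cut used for stratification: the below versus at-or-above threshold split is given only for the moderation analysis and should not be assumed to be the same one. If the omission is deliberate, one sentence of justification would do instead.

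The cost is a few phrases. Poverty status has to be known before randomisation, and income is collected at screening, so no new data are needed. The change should be recorded before outcomes are examined by arm, so that the added covariate cannot look data-driven.

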Aim II. Investigate the mechanisms through which mindfulness training impacts smoking cessation. Participants will complete questionnaires from baseline through 24 weeks after the start of treatment, in addition to intensive diary assessments for 6 contiguous weeks during treatment. We hypothesize that:

- 2a) Compared to UC, the mindfulness treatment arms (MBAT, iQuit Mindfully, and MBAT + iQuit Mindfully) will increase mindfulness; reduce negative affect (NA) and volatility of NA (i.e., greater affective stability); increase positive affect; reduce craving and withdrawal; and increase self-efficacy and social support, all of which will mediate effects of the mindfulness-based treatment arms vs. UC on abstinence.
- 2b) Compared to UC, MBAT, iQuit Mindfully, and MBAT + iQuit Mindfully will all attenuate links between NA/craving and smoking. That is, in addition to reducing NA and craving (2a), mindfulness training is hypothesized to weaken the relationships between NA/craving and smoking.

2c) Compared to MBAT, MBAT + iQuit Mindfully will produce stronger effects on the above mechanisms (2a, 2b). Mechanisms outlined in 2a will mediate effects of MBAT + iQuit Mindfully vs. MBAT on abstinence.

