6. STUDY PROCEDURES

6.1 Schedule of Treatment Procedures and Evaluations

			Weeks									
	Phone/ Online Screen	Base- line	1 Start of Tx	2	3	4	5	6	7	8 End of Tx	12 (3 Month Follow- Up)	24 (6 Month Follow- Up)
Telephone/Online Screening	Х											
Compensation			\$30		\$30		\$30			\$40	\$60	\$70
Electronic Diary Assessments		Every	other day	surveys 1	from week	2 to wee	k 8; \$5 pe	r survey 1	or up to \$1	20 total		
TREATMENT PROCEDURES												
Virtual MBAT groups (MBAT & MBAT + iQuit Mindfully conditions)			Tx 1	Tx 2	Tx 3	Tx 4	Tx 5	Tx 6	Tx 7	Tx 8		
iQuit Mindfully text messages (iQuit Mindfully & MBAT + iQuit Mindfully conditions)		Text messages based upon participants' choice in frequency and timing of messages										
Self-Help Materials (all conditions)		Χ	X									
Nicotine Replacement Therapy Dispensation (all)			Participants receive 4 weeks of patches and lozenges in person at baseline, and then the remaining 4 weeks of patches are mailed.									
IN-PERSON ELIGIBILITY												
Carbon Monoxide		Х								Х	Х	Х
Cotinine (Saliva Sample)												Х
Screening for Depression and Substance Dependence		Х										
SMOKING												
Information for Setting Up Text Messages		Х										
Tobacco History	Х											
Smoking Status, use of other tobacco products, electronic vapor products, NRT, pharmacotherapy		Х	Х		Х		Х			Х	X	Х

	Phone/ Online Screen	Base- line	1 Start of Tx	2	3	4	5	6	7	8 End of Tx	12 (3 Month Follow- Up)	24 (6 Month Follow- Up)
Additional Resources Used for Smoking Cessation										Х	X	X
Wisconsin Inventory of Smoking Dependence Motives (WISDM)		Х								Х	Х	Х
Wisconsin Smoking Withdrawal Scale (WSWS)			Х		Х		Х			Х	Х	Х
Self-Efficacy Scale		Х	Х		Х		Χ			Х	Х	Х
MINDFULNESS												
Mindfulness Attention Awareness Scale (MAAS)		Х								Х	Х	Х
Five Facet Mindfulness Questionnaire (FFMQ short form)		Х								Х	Х	Х
Mindfulness Practice Frequency					Х		Х			Х	Х	Х
Self-Compassion Scale (short form)		Х								Х	Х	Х
STRESS/ NEGATIVE AFFECT												
Perceived Stress Scale		Х								Х	Х	Х
Positive and Negative Affect Scale		Х	Х		Х		Х			Х	Х	Х
Experiences with Discrimination		Х										
SOCIAL SUPPORT												
Multidimensional Scale of Perceived Social Support			Х							Х	Х	Х
Group Climate Questionnaire (MBAT & MBAT + iQuit Mindfully)										Х		
PROGRAM EVALUATION												
Text Message Feedback					Х		Х				Х	Х
Perceived Benefits										Х	Χ	Х
Program Evaluation Questionnaire										X		

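### Section 9 does not put the participant's own baseline score into the Aim II and secondary-scale models, which costs precision on arm effects and leaves the mediator-to-abstinence path open to confounding

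*Combined protocol and SAP*

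**What the plan says.** Section 9 of the combined protocol and SAP gives a single adjustment rule: "All analyses will control for demographics (age, gender, race/ethnicity, education level, partner status) and baseline nicotine dependence". Dependence here means daily cigarette count and time to the first cigarette. The Aim I paragraph repeats the rule for the mixed model: "Fixed effects considered in each model will include demographics, baseline nicotine dependence, treatment condition and time as main effects, and a treatment condition by time"; the last of these terms is the arm-by-time interaction. That model is written for binary endpoints: "each dichotomous study outcome (smoking cessation, lapse recovery) will be assessed with a generalized linear mixed model (GzLMM"). No separate model is written for the continuous scales.

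For Aim II the plan says "Mediation will be examined with multilevel mediation analyses for binary outcomes in the developed GzLMM", so mediation inherits the same covariates. The data are described as "traditional questionnaire data (collected from baseline through 24 weeks after the start of treatment"), which includes the baseline wave but does not say how it enters. The only other stated use of baseline responses is in multiple imputation.

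Hypothesis 2a (Section 1) predicts that the mindfulness arms will raise mindfulness, "reduce negative affect (NA) and volatility of NA (i.e., greater affective stability"), raise positive affect, reduce craving and withdrawal, and raise self-efficacy and social support. All of these are expected to mediate abstinence against usual care.

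Table 6.1 marks seven scales at baseline: "Mindfulness Attention Awareness Scale (MAAS"), FFMQ-SF, Self-Compassion, PSS, PANAS, Self-Efficacy and WISDM. Section 4 places randomisation after the baseline assessments. The withdrawal scale (WSWS) and the social support scale are first marked at week 1, and Section 6.2 starts the diaries in week 2.

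**The concern.** The baseline score is usually the best single predictor of the later score on the same scale. Leaving it out of an arm-to-scale model gives up precision that costs nothing to obtain. It matters most in the contrasts with usual care, which has only 50 participants.

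The second issue is bias. Randomisation protects the arm-to-mediator path (a). It does not protect the mediator-to-abstinence path (b), because nobody is randomised to a level of mindfulness or confidence. People who start higher on a scale tend to stay higher, and they may also quit more for that reason. Without the baseline score, part of that association is read as an effect of the later mediator. The trial could then name a mechanism that treatment moves but that does not cause quitting.

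**Working it through.** **The plan's own figures.** 3 × 145 + 50 = 485, as stated. Section 9 also expects 80% power for mediation. It gives no mediated effect size, baseline correlation or covariate R², so that figure cannot be reproduced.

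**Check 1: arm effect on a scale**

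Inputs from Section 9: d=0.35 (mindfulness vs usual care), two-sided 0.05, 20% attrition. Completers are 145 × 0.8 = 116 and 50 × 0.8 = 40. Two assumptions are mine: the plan's d is carried over to a continuous scale, and the baseline-to-follow-up correlation r lies between 0.3 and 0.7. The calculation uses a single time point.

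- SE in SD units: √(1/116 + 1/40) = 0.1834.
- Unadjusted: 0.35/0.1834 = 1.909, so power = Φ(1.909 − 1.960) = 48%.
- Baseline as covariate: SE × √(1 − r²). At r=0.6, 1.909/0.8 = 2.386, so power = Φ(0.426) = 67%.
- Unconstrained change score: SE × √(2(1 − r)). At r=0.6, 1.909/0.894 = 2.134, so power = Φ(0.174) = 57%.

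| r | Unadjusted | Change score | Baseline as covariate |
|---|---|---|---|
| 0.3 | 48% | 36% | 52% |
| 0.5 | 48% | 48% | 60% |
| 0.6 | 48% | 57% | 67% |
| 0.7 | 48% | 69% | 76% |

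For two active arms (116 vs 116) at the same d, power is 76% unadjusted against 80/87/92/96% adjusted.

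**Check 2: false mediation**

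This was simulated at one time point. Baseline score X is standard normal. The later mediator is M = rX + √(1 − r²)·e + a·arm. Abstinence is about 20%, depends on X with log-odds g per SD, and does not depend on M (true b = 0). Path a was tested by linear regression of M on arm. Path b was tested by logistic regression of abstinence on arm and M. Each was run with and without X. Assumed values: r = 0.5 to 0.7, g = 0.3 to 0.5.

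| Setting | a and b both significant, without X | With X |
|---|---|---|
| a = 0.4 SD, 145 vs 50 | about 7-33% | about 3-6% |
| a = 0.4 SD, 435 vs 50 (three arms pooled) | about 19-66% | about 3-6% |
| a = 0, either comparison | about 1-5% | below 1% |

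With a = 0.35, g = 0.5 and 116 vs 40 completers, the false rate is 10-18% without X and 3-4% with it. If the confounder is a trait that X measures imperfectly, the rates are 18-25% and 9-10%.

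**Check 3: power for a true indirect effect**

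With a = 0.35, b = 0.4, r = 0.6 and 116 vs 116, adjustment raises path-a power from about 75% to 90-91%. Power for the indirect effect moves from 51-52% to 44-45%. Here adjustment removes bias without adding power.

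**The case against.** The covariate sentence does not call itself exhaustive, the fixed-effects list is written for binary endpoints, and the baseline wave is in the Aim II data. The analysts may intend to use it. This stands to the extent that the defect is an unstated role for baseline, not a declared refusal to use it. If baseline enters as a repeated response with means constrained equal across arms, essentially all the arm-to-scale precision is recovered. An unconstrained change score recovers much of it at r = 0.6 to 0.7, none at r = 0.5, and loses power at r = 0.3. None of these adjusts the mediator-to-abstinence path.

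A reader might infer that stable traits alone would pass as mediation. They would not. Arms are balanced at baseline in expectation, so if treatment does not move the scale the expected indirect effect is zero and the false rate stays near 1-5%. The large rates need a real arm effect on the scale, which hypothesis 2a does predict.

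A reader might also infer that the omission costs power for mediation. Check 3 does not support that. Nor can the plan be said to contain faulty models for the secondary scales, because none is written.

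Finally, d = 0.4, r, g and the abstinence rate are assumptions, and 0.4 exceeds the plan's own 0.33-0.35. The direction of the result does not depend on them, but its size does.

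**Conclusion.** The concern holds in limited form. Section 9 does not specify adjustment for the baseline score of the mediator or secondary scale, although seven relevant scales are measured before randomisation. At the plan's own d, power for a usual-care contrast on a scale is 48% unadjusted and 52-76% adjusted, depending on r. Where treatment moves a scale that does not drive quitting, the risk of a false mechanism claim falls from roughly 7-33% (145 vs 50) or 19-66% (435 vs 50) to about 3-6% if the baseline score carries all the confounding. If it measures the trait imperfectly, some excess remains. WSWS craving and withdrawal, social support and the diary measures have no pre-treatment value, so the remedy cannot reach them. The point concerns Aim II and the secondary scales; it does not question the primary abstinence comparison.

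**What to change.** Add to Section 9:

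- *Each model of a mediator or continuous secondary outcome, and each mediator-to-abstinence model using questionnaire data, includes the baseline value of that measure as a covariate where Table 6.1 collects it (MAAS, FFMQ-SF, Self-Compassion, PSS, PANAS, Self-Efficacy, WISDM). For arm effects on a scale, baseline may instead be a repeated response with means constrained equal across arms.*
- *WSWS, social support and diary mediators have no pre-treatment value. Their mediator-to-abstinence results are reported as more open to confounding.*

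The same edit should write out the model for the continuous scales, which is now missing. In the diary analyses, separating within-person from between-person mediator effects would help where no baseline exists.

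The cost is a few sentences in the SAP. The baseline data are already scheduled, so there is no added visit, questionnaire or participant burden.
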